12.1. Type of Resources

Many resources will be necessary to ensure the success of this project. There are three types of resources: human resources, material resources, which can be fungible or inventoriable, and other resources. The principal researcher, research assistants, a statistician, outcome assessors, physiotherapists and participants are among the human resources (Table 3). Material resources (Table 4) include equipment for doing the intervention, the data administration and the statistical analysis, such as questionnaires, physiotherapy material, computers and software. Lastly, other resources (Table 5) include the fees and miscellaneous. The needed resources for this project are mentioned in the tables below (Tables 3-5), along with their quantity, availability and estimated cost. These tables are designed to serve as a guide to ensure that all necessary resources are accounted for and that their budget is properly allocated being subjected to changes if needed.

Human Resources					
Role	Quantity	Salary (€/month)	nº Month	Estimated Cost	Availability
Principal Research	1	750	16	12.000,00 €	Myself
Research Assistant	2	600	10	12.000,00 €	Need to hire
Statistician	1	700	1	700,00 €	Need to hire
Physiotherapist	4	1.200	4	19.200,00 €	Need to hire
Outcome Assessor	2	600	1	1.200,00 €	Need to hire
Participant	60	-	-	-	Need to recruit
Total Cost				45.100,00 €	

Table 3: Human Resources description and estimated budget

Material Resources					
Resource	Description	Type	Estimated Cost	Availability	
Play-Therapy equipment	Different size and texture balls, sensory toys, adaptative toys, music equipment...	Inventoriable	500,00 €	Need to purchase	
Physiotherapy equipment	Positioning equipment, balance boards, different size roller, tunnels...	Inventoriable	- €	Available in the centre	
Physiotherapy consumables	Gloves, alcohol wipes, massage cream, disposable paper towels...	Fungible	- €	Available in the centre	
Office supplies	Paper, ink, pencils, pens...	Fungible	200,00 €	Need to purchase	
IT Equipment	3 laptops	Inventoriable	- €		
Data collection	Logbooks, GMFM App+, GAS sheet	Fungible	1.000,00 €	Need to purchase	
Data storage	OneDrive	Inventoriable	495,00 €	Need to purchase	
Data management	JASP Software	Inventoriable	Free	Need to purchase	
Total Cost			1.700,00 €		

Table 4: Material Resources description and estimated budget

Other Resources		
Resource	Description	Estimated Cost
Ethical approval fees	Charged by an IRB for review of research proposals	1.000,00 €
Insurance fees	To protect against any accidents or injuries that may occur during the study	500,00 €
Publication fees	For publishing papers, posters, or other materials related to the project	1.500,00 €
Miscellaneous	Travel expenses, equipment maintenance and repairs, communication expenses...	1.000,00 €
Total Cost		4.000,00 €

Table 5: Other Resources description and estimated budget

[figure not shown]
Table 6 shows the final cost estimation and offers an extensive overview of the budget for each type of resource. The budget for the project, as shown graphically in Graphic 1, mainly goes to managing and carrying out the study, including paying the researcher and research assistants their salaries. Since those working in these roles may be PhD students or research interns, universities or research institutions may in certain cases cover these costs. The last option would be recruiting volunteers.

Each physiotherapist will be responsible for conducting two sessions per week with 16 children, with each session lasting for a range of one hour (45 minutes for the session itself and 15 minutes for completing the logbook and registering the session). As a result, the physiotherapists will work for a total of 32 hours per week, and their monthly salary will be 1200€.

Total Estimated Budget	
Resource	Total Estimated Cost
Human Resources	44.800,00 €
Material Resources	2.033,00 €
Other Resources	5.000,00 €
Total Cost	51.833,00 €

Table 6: Total Estimated Budget

Total Estimated Budget

Graphic 1: Total Estimated Budget

12.2. Foundation

Finding appropriate funding sources can be a difficult task, but financial support is an essential aspect of research. The potential foundations listed in this section describe how my research project might be funded.

There are two ways that may be used to control the project's potentially large budget. First, looking into the foundation options (Table 7) might be taken into consideration. On the other hand, in order to lower the cost of the research study, it is also possible to apply for a pre-doctoral internship, which not only offers financial help but also improves research abilities (Table 8).

Foundation Name	Focus Area	Deadline	Grant Amount
La Marató de TV3	Biomedical research in Catalonia related to specific topics	Every March	Up to 400.000€
Fundación “La Caixa”	Supports research in healthcare	Every March	Up to 50.000€
Fundación Maphre	Biomedical research of specific topics	Every October	Up to 30.000€
Col·legi de Fisioterapeutes de Catalunya	Physiotherapy research of specific topics	Every September	Up to 6.000€

Table 7: Foundations for Research Funding

Institution Name	Description	Duration	Salary
Fundación “La Caixa”	Provides funding for pre-doctoral research in any university of Europe	3 years	40.000€
Fundació Universitària del Bages (FUB) - Campus Manresa	Provides funding for the doctoral thesis in their research department	3 years	18.000€
Universitat de Vic – Universitat Central de Catalunya	Provides funding for the doctoral thesis in their research department	3 years	17.500€

Table 8: Pre-doctoral Internships in Physiotherapy in Barcelona

13. Applicability and Usefulness of the Results

The applicability and usefulness of this project's outcomes are important for multiple reasons. To begin, cerebral palsy is a chronic disorder that impairs children's ability to move, perform daily tasks and participate in life. Physiotherapy is a significant part of cerebral palsy treatment since it tries to enhance function and minimize secondary complications. When compared to conventional physiotherapy, the use of play-based physiotherapy has been suggested as a potentially more successful strategy to engage children in therapy and promote treatment adherence while improving gross motor function. So, the results of this randomized controlled study will aid in determining if the hypothesis is correct. That's why if the study reveals that is more successful, it might have significant implications for the development of new interventions and treatment protocols for children with CP, which is the main goal of this project.

Furthermore, the identification of potential factors that may influence treatment outcomes is also valuable for improving treatment approaches in the future. By identifying these potential factors, physiotherapists can develop more tailored treatment plans considering the unique needs and circumstances of each patient. All in all, this can help to improve treatment outcomes and ensure that they receive the most effective and tailored physiotherapy program. For example, if this study shows that children from poor socioeconomic status or an specific ethnic group respond better to play therapy-based physiotherapy program or vice versa, physiotherapist may adapt treatment techniques to these specific populations to be more tailored and equitable.

Lastly, in case that the hypothesis is found to be wrong, the methodology of the study, including the inclusion and exclusion criteria and the use of stratified randomization, will add to the domain of cerebral palsy research and serve as a model for future studies as well as the study's emphasis on incorporating individuals from a variety of socioeconomic situations and ethnicities will assist to guarantee that the findings are applicable to a broad range of children with cerebral palsy. Moreover, the study's attention on ethical issues, such as getting informed consent and providing fair access to the study, will contribute to the general ethical standards and best practices in this field.

14. Dissemination Plan

In this section I will show you the steps that will be conducted to do the dissemination of the project and its results. The purpose of this is to outline the strategies and activities that will be used to disseminate the findings of the research project to ensure that the results of this study reach relevant stakeholders, such as healthcare professionals, parents/caregivers of children with cerebral palsy, and other researchers in the field of paediatric rehabilitation.

Firstly, once the study is finished and the final report is written, I will submit it to a peer-reviewed journal in the field of paediatric rehabilitation, physiotherapy, and cerebral palsy. This will enable to disseminate the findings to a broader audience of healthcare professionals and researchers, and to contribute to the knowledge base on this topic. Also, this ensures that the project is evaluated and criticised by other experts in the field, increasing its visibility and credibility.

Journal	Description	Impact Factor (IF)	Q level
Developmental Medicine & Child Neurology	Publishes high-quality multidisciplinary research and is highly respected and well-regarded	4.864	Q1
BMC Pediatrics	It's an open access journal and publishes research on all aspects of paediatrics. It has a strong reputation	2.567	Q2
Journal of Neurologic Physical Therapy	Dissemination linked to neurologic physical therapy. Excellent quality maintained by a rigorous, double-blind peer-review procedure	4.741	Q1
Physical and Occupational Therapy in Pediatrics	Provides important information to physiotherapist and occupational therapists in the developmental and physical rehabilitation of new-borns, children, and teenagers	2.297	Q2

Table 9: List of the journals, their description, Impact factor and Q level.

In the previous table (Table 9), we can see a list of the journals to which I would submit the project report, their order, and the reason for their selection, all this information is extracted from Scimago Journal & Country Rank (E). I would start with the first option (Developmental Medicine & Child Neurology), and in case of rejection, I would make the necessary corrections suggested by the first journal and then submit it to the second option. I would continue this process until one of these journals accepts the project. If none of these journals accepts it, I would look for other similar journals of lesser importance.

Simultaneously, a poster will be created to present it at national and international conferences and congresses related to paediatric rehabilitation, physiotherapy, and cerebral palsy (Table 10). This will allow reaching a wide audience of healthcare professionals and researchers, and to receive feedback and engage in discussions about the implications of the findings.

Congress	Description	Periodicity
World Physiotherapy Congress	brings together physiotherapists from around the world to share knowledge, research and ideas on a variety of topics related to physiotherapy.	Each two years
European Academy of Childhood Disability Conference	This international conference brings together healthcare professionals, researchers, and families to share knowledge and best practices related to childhood disability	Annually
Congrès Internacional de Fisioteràpia	Is a congress focused on physiotherapy that takes place in Barcelona and the aim is shearing knowledge and best practices related to physiotherapy	Each two years

Table 10: List of the congresses, their description and periodicity.

E. Scimago Journal & Country Rank [Internet]. Scimagojr.com. [cited 5 of April 2023]. Available in: <https://www.scimagojr.com/>

Finally, a webinar could be conducted to share the results of the study with parents/caregivers of children with cerebral palsy, CP rehabilitation centres, and other interested parties. The objective is to disseminate the findings directly to the people who are most affected by this condition as a way of recommendation and to engage in a dialogue about the implications of the research for their daily lives.

15. Annexes

15.1. Annex I: Calculation of the Sample Size

For calculating the sample size the following formula have been used (F, G):

$$n = \frac{2SD^2(Z_{\alpha/2} + Z_{\beta})^2}{d^2}$$

Where:

- **n** = sample size
- **Z $\alpha/2$** = the Z-score for the desired level of significance so for 95% confidence level $\alpha=0.05$, $Z_{\alpha/2} = 0.05/2 = 0.025$. This from Z table is **1.96**.
- **Z β** = the Z-score for the desired statistical power so for 80% power where β is 0.20, $Z_{\beta} = 0.8416$ from the Z table.
- **SD** = the estimated standard deviation of the outcome variable based on other studies is **2.43** (18).
- **d** = the effect size (difference in means divided by the pooled standard deviation) taking into account the previous study (18) it will be **1.2**.

Having into account all this, the sample size should be:

$$n = \frac{2SD^2(Z_{\alpha/2} + Z_{\beta})^2}{d^2}; n = \frac{2 \times 2.43^2 (1.96 + 0.8416)^2}{1.2^2}; n = 64.37 \approx 64 \text{ participants}$$

Sample size = 64 participants.

Remember that this sample size may need to be adjusted by a statistician based on factors such as recruitment rate and expected dropout rate.

F: Charan J, Biswas T. How to calculate sample size for different study designs in medical research? Indian J Psychol Med. 2013 Apr;35(2):121-6.
G. Kadam P, Bhalerao S. Sample size calculation. Int J Ayurveda Res. 2010 Jan;1(1):55-7.

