9.2. Participants, Recruitment and Criteria of Selection

9.2.1. Participants

The participants of this research will be children with CP GMFCS level III-IV, aged 4 to 12 years and receiving physiotherapy services.

For the sample size ([Annex I](#)), help will be requested from a statistician, and it will depend on factors such as the expected effect size based on previous studies or clinical knowledge, the level of statistical power desired and the level of significance. For example, knowing that similar studies have a sample size of 30, which is always their limitation, a medium effect size is expected, a power of 80% is desired and 0.5 is considered as the level of significance, a sample size of around 64 participants (32 in each group) might be appropriate. However, this sample size might need to be adjusted based on the recruitment rate, dropout rate, and effect size observed during the study.

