9.6. Data Analysis

All data collected from the assessments, questionnaires and the logbook will be analysed using appropriate statistical methods with the help of an expert statistician to achieve the aims of this research protocol. The statistical analyses will be conducted using a statistical software package such as JASP and the statistical significance will be set at p-value <0.05 and CI (Confidence Interval) 95%. When p-value $< 0,05$, the null hypothesis (H_0) will be rejected meaning that the results are statistically significant. The H_0 is: There is no significant difference between the effectiveness of play therapy-based physiotherapy programs and conventional physiotherapy programs in improving treatment adherence and gross motor function in children with cerebral palsy GMFCS level III-IV.

After collecting all data, it will be placed into a spreadsheet for basic data cleaning and categorization ([Annex V](#)). Descriptive statistics (e.g., mean, median, standard deviation, range...) will be calculated to summarize quantitative variables such as age, attendance rate, treatment adherence logbook, GAS score, GMFM-88 score and CP QOL-Child score, while frequency distributions and percentages will be used to summarize categorical variables such as gender, GMFCS level (III or IV), socio-economic status, ethnicity, and type of intervention. All that describes the participants' demographic and baseline characteristics, as well as analyses the distribution of the variables of interest.

Statistical analysis will be done to test the hypothesis using appropriate methodologies based on the data distribution and characteristics. For quantitative variables, t-tests or ANOVA may be used to compare means between the two groups (play therapy-based physiotherapy versus conventional physiotherapy). However, for categorical variables, chi-square or Fisher's exact test might be used, but in this study, it may not be necessary as the hypothesis doesn't include categorical variables.

Moreover, linear regression analysis may be used to investigate the association between treatment adherence and gross motor function while to identify predictors of treatment adherence, gross motor function and quality of life, including age, gender, GMFCS level, social-economic status, ethnicity, and treatment group so potential confounding variables will be controlled for in the

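### Annex I's formula gives 64 children per group, but the protocol enrols 64 in total (32 per group), so power on its own inputs is about 49%, not the stated 80%

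*Protocol*

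**What the plan says.** Annex I (section 15.1) sets out n = 2·SD²·(Zα/2 + Zβ)²/d². It takes Zα/2 = 1.96, Zβ = 0.8416 ("the Z-score for the desired statistical power so for 80% power where β is 0.20"), SD = 2.43 and d = 1.2. It describes n only as the sample size, without saying per group or total. It describes d as "the effect size (difference in means divided by the pooled standard deviation" (the bracket closes there). The result is 64.37, rounded to 64, with the conclusion "Sample size = 64 participants".

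Section 9.2.1 expects a medium effect, asks for 80% power and says that "a sample size of around 64 participants (32 in each group) might be appropriate". The abstract also gives 64 children for the whole trial. The staffing in section 12.1 agrees: four physiotherapists with 16 children each make 64.

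On the significance level, section 9.2.1 says "0.5 is considered as the level of significance". Annex I works with 0.05, and section 9.6 says "the statistical significance will be set at p-value <0.05 and CI (Confidence Interval) 95" (per cent).

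**The concern.** The factor 2 in the formula is there because the variance of a difference between two independent means is the sum of two variances. The n it returns is therefore the number in each group. Reading it as the total halves the trial that the calculation supports.

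Three other statements make the calculation hard to rely on:

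- d is labelled as already divided by the SD, yet the SD is still in the numerator.
- The significance level is given in two different values.
- Annex I does not say to which outcome the SD of 2.43 belongs, although section 9.4 names two primary outcomes, adherence and gross motor function, on different scales.

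At stake is the main quantitative justification of the trial. Families and the ethics committee would be told 80% power for a medium effect, while such an effect would be missed about half the time. Section 9.6 says that conclusions will rest on statistical significance, so a non-significant result from this design could easily be over-read. Section 9.7 admits a small sample, but only as a limit on generalisability, not on power.

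**Working it through.** **Inputs.** From Annex I: SD 2.43, d 1.2, Zα/2 1.96 (two-sided 0.05), Zβ 0.8416 (80% power). From section 9.2.1: 32 per group and a medium effect. From section 9.6: means of two groups compared by t-test or ANOVA.

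**1. Reproduce the plan's figure.**

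n = 2 × 2.43² × (1.96 + 0.8416)² / 1.2² = 2 × 5.9049 × 7.8490 / 1.44 = 92.695 / 1.44 = 64.37.

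The printed number is reproduced, and it is the size of one group. Rounded up it is 65 per group. The total is 2 × 64.37 = 128.7, or 130 with whole children in equal groups. The t-test, slightly stricter than the normal approximation, needs 65.3, so 66 per group (132).

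**2. Which meaning of d fits?**

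- As a raw difference: 1.2 / 2.43 = 0.494 SD. This agrees with the medium effect in section 9.2.1 and with keeping the SD in the formula.
- As a standardised effect of 1.2: the SD drops out and n = 2 × 7.849 / 1.44 = 10.9 per group (about 12 by the t-test). That does not give 64 and is not a medium effect.

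Only the raw reading is consistent with the stated calculation.

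**3. Power actually available** (two-sided 0.05, two-sample t-test by the noncentral t, difference 1.2, SD 2.43):

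| Children per group | Power |
|---|---|
| 32 (as planned) | 49.4% |
| 64 | 79.2% |
| 65 | 79.8% |
| 66 | 80.4% |

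The normal approximation gives 50.6% at 32 per group. With an effect of exactly 0.5 SD the t-test gives 50.4% at 32 per group and 80.1% at 64, so the main text's medium effect leads to the same place.

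**4. Detectable effect.** With 32 per group, 80% power by the t-test needs 0.711 SD; 0.711 × 2.43 = 1.73 in raw units, against the planned 1.2.

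**5. Dropout.** The protocol applies no allowance. Assuming 10%, 15% or 20% loss, power at 1.2 falls to about 45%, 43% or 41%. Table 3 budgets for 60 participants; 30 per group gives 47%.

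**6. The 0.5.** With alpha 0.5 (Z = 0.6745) the formula gives 2 × 5.9049 × (0.6745 + 0.8416)² / 1.44 = 18.9. The calculation therefore used 0.05, and the 0.5 in section 9.2.1 is a misprint with no effect on the number.

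**The case against.** **d is defined as standardised.** Taken literally, an effect of 1.2 SD would give 99.7% power with 32 per group. The source of 1.2 is a cited study that is not at hand, so the 49% depends on reading d as a raw difference. That condition stands and should be stated. The literal reading does not rescue the annex, however: it conflicts with keeping the SD in the formula, with the result of 64 and with the medium effect. Annex I is wrong as written on either reading.

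**Adjustment for baseline could recover power.** The abstract lists ANCOVA, and the GMFM-88 is measured at baseline. Assuming a baseline–outcome correlation of 0.5, 0.6 or 0.7, power at 32 per group is about 61%, 68% or 78%; reaching 80% needs about 0.72. This is a fair qualification for gross motor function. But Annex I takes no such credit, section 9.6 names t-tests or ANOVA for the group comparison, and the adherence logbook is filled in after treatment sessions, so it has no pre-treatment value to adjust for.

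**A one-sided test.** Annex I uses 1.96, which is two-sided. One-sided 0.05 would still give only 62% at 32 per group.

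**The text is tentative and foresees adjustment by a statistician.** True, but the adjustments named concern recruitment, dropout and observed effect. None concerns the confusion of group size with total, and the abstract states 64 without reservation.

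**Section 13.** It says only that the methods would still be useful if the hypothesis proved wrong. It sets no rule that a non-significant result disproves the hypothesis. The interpretive risk comes from section 9.6, and it is secondary to the arithmetic.

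**Conclusion.** The concern holds. Annex I's 64.37 is a per-group number used as a total. For the annex's own inputs, with d taken as a raw difference of 1.2 and an unadjusted two-sided t-test at 0.05, the planned 32 per group gives about 49% power instead of 80%. The trial is about half the size that its formula asks for, before any dropout. Baseline adjustment might raise power for gross motor function, but the documents give no correlation and claim no gain. The mislabelled d and the unnamed outcome are part of the same defect. The 0.5 is a misprint that adds nothing to its size. This must be corrected before the 80% figure is relied on.

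**What to change.** In Annex I:

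- Label n as the number per group.
- Define d as the difference in means in the units of the outcome.
- Name the primary outcome to which SD 2.43 and d 1.2 apply.

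In section 9.2.1, change 0.5 to 0.05.

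Then choose one of two courses and state it identically in the abstract, section 9.2.1 and Annex I:

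- **Keep 64 in total.** Suggested wording: 64 children (32 per group) give about 49% power for a difference of 1.2 (SD 2.43) and 80% power for a difference of 1.73 (0.71 SD), two-sided alpha 0.05, before dropout. The cost is wording only, with a less favourable power statement. If baseline adjustment is to be credited, state the assumed correlation and its source.
- **Keep 80% power for 1.2.** Plan 65 per group by the annex's formula (66 by the t-test), so 130 to 132 children plus a stated dropout allowance. This roughly doubles recruitment and the physiotherapist time in section 12.1.

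Under either course, add to section 9.6 that a non-significant result will be reported with its confidence interval and not taken as evidence that the programmes are equally effective.
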